In orthodontic treatment, achieving proper alignment of anterior teeth is a key objective.⁶ Different ligation methods, such as elastomeric and steel ligatures, have been employed to achieve alignment.⁷ Elastomeric ligatures are preferred by orthodontists due to their ease of use and reduced chairside time, but the effectiveness is reduced overtime due to absorption and friction.⁸ Steel ligatures on the other hand require manual twisting of wire thereby increasing chairside time but provide effective engagement of wire into bracket slot and provide low friction mechanics.⁹ The duration of treatment is an important factor for both patients and orthodontists, as it can impact overall treatment efficiency and patient satisfaction.¹⁰ In a study by Reddy et al on comparison of different ligation method on time to reach alignment reported that the mean treatment time for alignment in elastomeric ligature was 176.3 ± 11.08 days while in steel ligature was 175.56 ± 9.41 days.¹¹ Another study reported the mean treatment time for alignment in elastomeric ligature was 224.95 ± 8.702 days while in steel ligature was 176.15 ± 9.81 days.¹²

This study aims to compare the mean treatment time required to achieve alignment of anterior teeth using elastomeric ligatures versus steel ligatures. By evaluating and analyzing these two

commonly used ligation techniques, we can gain valuable insights into their respective effectiveness in facilitating the alignment of anterior teeth. Owing to the contradictory results of the aforementioned studies this study would put to rest the contradictions. Ultimately, the findings from this study may contribute to informed decision-making regarding ligation methods, optimizing treatment outcomes, and enhancing patient experiences in orthodontic practice. There is lack of research on this topic in Pakistan, so this study will provide local statistics. The results can be variable across different populations due to genetic, ethnic and environmental factors.

OBJECTIVE

To determine the mean treatment time required by elastomeric ligatures and steel ligatures, in days, to achieve complete alignment of the lower anterior teeth.

OPERATIONAL DEFINITIONS

1. Littles irregularity index:

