Measure of the distance in mm, using a Castroviejo caliper, of the sum of horizontal displacements of the anatomical contact points of the mandibular anterior teeth. It will be recorded as 0 (Perfect alignment), 1-3 (Minimal irregularity), 4-6 (Moderate irregularity), 7-9 (Severe irregularity), 10 (Very severe irregularity)

2. Alignment:

Littles irregularity index score of zero. Calculated by summing the distances (in mm) of the horizontal displacements of the anatomical contact points of the mandibular anterior teeth.

3. Elastomeric ligature:

O- shaped synthetic elastic of 0.1" diameter that holds the archwire in bracket slots.

4. Steel ligature:

Soft grade stainless steel wire of 0.009" thickness that holds the archwire in bracket slots.

OUTCOME

To determine the mean treatment time required by elastomeric ligatures and steel ligatures

RESEARCHER'S HYPOTHESIS

The treatment time taken to complete alignment of lower anterior teeth is shorter in steel ligature ligation than elastomeric ligature.

MATERIALS AND METHODS

Study Design: Randomized Clinical Trial

Setting: Department of Orthodontics and Dentofacial Orthopedics, Khyber College of Dentistry Peshawar.

Duration: 6 months after approval of synopsis.

Sample Size: By using Openepi,¹³ assuming the mean duration of 224.95 ± 8.7 days for Elastomeric ligature group and mean duration of 219.95 ± 9.82 days for steel ligature group¹², a sample of 90 participants per group will detect a 5 days difference in mean duration, with 95% power at 5% significance level.

Sampling Technique: Consecutive, Non-probability.

Inclusion criteria

1. Patients coming for fixed orthodontic treatment requiring premolar extraction in mandibular arch.
2. Age 12-18 years.
3. No adjunct therapeutic intervention involving functional or orthopaedic appliances.
4. Little's Irregularity index score of 7-9mm.

Exclusion criteria

1. Patients with systemic conditions and taking medications affecting tooth movement.
2. Lower anterior teeth that are missing, impacted or unerupted, or have fractured crown, restorations, Enamel Defects, Caries.
3. Poor periodontal health

DATA COLLECTION PROCEDURE

Approval of the hospital ethical committee will be taken. Patients from Orthodontics department, Khyber College of Dentistry fulfilling the inclusion criteria will be invited to take part in the study. The purpose, procedures, risk and benefits of the study will be explained to them. An informed written consent will be taken.

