The subjects fulfilling inclusion criteria will be assigned to one of two groups using lottery method. Group A will receive steel ligature, while Group B will receive elastomeric ligature for wire engagement in brackets. All participants will be bonded with a metal 0.022" slot of MBT pre-adjusted appliances. Archwire sequence will be 0.012 NiTi, 0.014 NiTi, 0.018 NiTi and 0.019x0.025 NiTi until alignment is reached. Adjustment appointments will be conducted at six-week intervals. Mandibular dental casts will be taken on the day of appliance placement (T1) and then on the day when alignment is reached (T2). Littles irregularity index will be calculated on mandibular casts using Castroviejo caliper. The alignment time from the day of appliance placement to the day when alignment is reached (T2-T1) for each participant will be recorded in days. All the above-mentioned information will be recorded in predesigned proforma (see Annex I).

Bias and confounders will be controlled in the study by strictly following inclusion/exclusion criteria, and randomization. Effect modifiers include gender, age and pre-treatment irregularity, which will be controlled by randomization.

Statistical Analysis:

Data will be analyzed using SPSS (statistical package for social sciences) version 25.0. Mean and standard deviation will be calculated for numerical explanatory variables like age and time to reach alignment. Frequency and percentage will be calculated for qualitative explanatory variables like gender. Independent Samples t Test will be applied to compare time of alignment in days between two groups (steel and elastomeric) at T2. Normality of data will be checked through Shapiro-Wilk Test. In case of skewed data Mann-Whitney U test will be applied instead of independent samples t test. Confounders like age and gender will be controlled through stratification. Post- stratification Independent Samples t Test/ Mann-Whitney U test will be applied. P value less than or equal to 0.05 will be considered significant.

REFERENCES

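### Age and gender are controlled only by repeating significance tests within strata, which gives no adjusted treatment effect and no test of effect difference; baseline irregularity is not named in the analysis section

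*Combined protocol and SAP*

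**What the plan says.** The primary comparison in the Statistical Analysis section is an unadjusted independent-samples t test of days to alignment, with a Mann-Whitney U test if the data are skewed. On covariates the section then says "Confounders like age and gender will be controlled through stratification", and the method offered is "Post- stratification Independent Samples t Test/ Mann-Whitney U test will be applied". One significance rule covers every test: "P value less than or equal to 0.05 will be considered significant". The section gives no age cut-points, pooled stratum-weighted estimate, regression model, interaction test or multiplicity rule.

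Just before that section, the Data Collection Procedure says "Effect modifiers include gender, age and pre-treatment irregularity, which will be controlled by randomization". Age and gender are therefore called both effect modifiers and confounders. Baseline irregularity is in the first list and is recorded in mm on the proforma (Annexure I), but the Statistical Analysis section does not name it. Because that section's list of confounders is open-ended, irregularity is not ruled out either; its role is simply unclear.

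**The concern.** Adjusting for age and gender should end in one treatment effect that takes them into account. Testing each stratum separately produces several P values and no such estimate, so the promised control is not delivered.

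Nor do separate tests address effect modification. Randomisation balances covariates in expectation, but it neither removes nor tests a difference in effect between boys and girls or between younger and older patients. Finding P ≤ 0.05 in one stratum and P > 0.05 in another is not evidence of such a difference, because each stratum has less power than the whole trial and the two results often disagree by chance.

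The likely consequence is a report that the ligature type matters in one gender or age band only. The introduction presents the trial as a way to settle conflicting earlier results, and a spurious subgroup finding would add another conflict. Age bands left open until the data are seen would make this easier.

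**Working it through.** **Inputs.** From Sample Size: SDs of 8.7 days (elastomeric) and 9.82 days (steel), 90 per arm, a 5-day difference, 95% power, 5% significance. From the introduction, two earlier results: "elastomeric ligature was 176.3 ± 11.08 days while in steel ligature was 175.56 ± 9.41 days" (difference 176.3 − 175.56 = 0.74 days) and "elastomeric ligature was 224.95 ± 8.702 days while in steel ligature was 176.15 ± 9.81 days" (difference 224.95 − 176.15 = 48.8 days). The gender split and the number of age bands are not in the documents and are assumed below.

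**The plan's own figure.** n per arm = (1.96 + 1.645)² × (8.7² + 9.82²) / 5² = 12.996 × 172.12 / 25 = 89.5, so 90. The plan's sample size reproduces with a two-sided test. Power from the t distribution at 90 per arm is 94.9%.

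**Power within strata.** The effect is 5 days in everyone; two-sided Welch t test at 0.05.

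| n per arm in stratum | Power |
|---|---|
| 90 (whole trial) | 0.949 |
| 60 | 0.833 |
| 54 | 0.792 |
| 45 | 0.715 |
| 36 | 0.616 |
| 30 | 0.537 |

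**Chance that exactly one gender is significant although the effect is identical in both.** With stratum powers p1 and p2 this is p1(1 − p2) + p2(1 − p1). For equal strata at 5 days: 2 × 0.715 × 0.285 = 0.408.

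| True effect in everyone (days) | Exactly one of two equal gender strata significant |
|---|---|
| 0.74 | 12% |
| 2.5 | 37% |
| 3.9 (peak) | 50% |
| 5 (planned) | 41% |
| 6 | 24% |
| 7.5 | 6.5% |
| 10 | 0.2% |
| 48.8 | essentially 0 |

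The figure is 25% or more between about 1.8 and 5.9 days. At 5 days it is 43% with a 60:40 split (0.792 × 0.384 + 0.616 × 0.208) and 48% with 2:1 (0.833 × 0.463 + 0.537 × 0.167).

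**No true effect.** This was simulated with 180 participants, random 50:50 gender and equally likely age bands.

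| | Two age bands | Three age bands |
|---|---|---|
| Overall test significant | 5% | 5% |
| Some gender or age stratum significant, overall test not | 12% | 16% |
| Any test significant, overall included | 17% | 21% |

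**What a direct comparison of strata could show.** The standard error of the overall difference is √(172.12 / 90) = 1.383 days. With two equal strata, the standard error of the difference between the stratum effects is 2 × 1.383 = 2.77 days. Its 95% interval is ±1.974 × 2.77 = ±5.5 days, wider than the effect the trial was designed to find.

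**Precision gain from adjustment.** The half-width of the 95% interval is approximately 1.96 × 1.383 × √(1 − R²), where R² is the share of outcome variance explained by the covariates. The documents do not give R². The half-width is 2.71 days at R² = 0, 2.57 at 0.10 and 2.35 at 0.25.

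**The case against.** The strongest reply is that the main result is untouched. The objective and the hypothesis concern only the overall difference between ligatures, and a randomised comparison needs no covariate adjustment to be unbiased. The plan nowhere says that strata will be compared or that a stratum result can stand in for the overall one. All of this stands, and it limits the point to the supplementary analyses. It does not rescue those analyses: the plan neither labels them exploratory nor exempts them from its significance rule, and they do not supply the control they are said to supply.

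A second reply is that adjustment will gain little precision, since entry is restricted to ages 12 to 18 and to an "Irregularity index score of 7-9mm". That is probably right. The case for the model is one interpretable adjusted estimate, not a narrower interval.

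A third is that the figures depend on the plan's SDs and on 90 complete outcomes per arm. Adjustment visits are six weeks apart. If alignment were recorded only at visits (an assumption), times would cluster near 210 and 252 days, and means of about 220 to 225 would imply SDs of about 18 to 20. At an SD of 19, overall power at 5 days is about 42% and the peak moves to about 7.5 days; discordance at 10 days is about 42% rather than 0.2%. The stated duration of 6 months, against planned means above 219 days, also leaves complete outcomes in doubt. So the 1.8-to-5.9-day range holds only under the plan's own SDs. At 5 days, however, discordance is still about 36%, and the conclusion survives.

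Finally, a linear model has no counterpart to the Mann-Whitney option. That is fair, and the fix below covers it.

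**Conclusion.** The concern holds and should be acted on, as an inexpensive improvement to the secondary analyses. The primary comparison remains valid.

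The planned stratification yields no effect adjusted for age and gender, whatever the true effect is. The risk of a false subgroup contrast depends on that effect. It is about 41% for gender at the 5 days for which "a sample of 90 participants per group will detect a 5 days difference in mean duration", peaks at 50% near 3.9 days, and is negligible at 10 days or more. At 0.74 days it is 12%. With no effect at all, a significant gender or age stratum alongside a negative overall test still occurs in 12% to 16% of trials.

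These figures assume the plan's SDs, complete data on 90 per arm, a 50:50 gender split, the same effect in everyone and, for the no-effect figures, two or three age bands.

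**What to change.** Keep the overall comparison as the primary analysis and rewrite the rest of the paragraph:

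- Replace the post-stratification tests with one prespecified secondary linear model of days to alignment on group, baseline Little's index (mm), age (years, continuous) and gender. Report the adjusted mean difference with its 95% confidence interval.
- State in advance what will be done if the residuals are clearly skewed, for example robust or bootstrap standard errors.
- Show any gender or age stratum results as mean differences with 95% confidence intervals, with age bands fixed beforehand and no significance verdicts.
- Label any group-by-covariate interaction exploratory, given its interval of about ±5.5 days.

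Age, gender and baseline irregularity are already on the proforma, so no new data are needed, and the adjustment does not call for more than 90 per arm. The cost is a rewritten analysis paragraph and one additional model with its checks. The change does not deal with participants who have not reached alignment by the end of the study; the plan must handle those separately.

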1. Littles irregularity index before treatment: _____ mm

2. Lower brackets bond up (T1), Dated: _____ / _____ / _____.

3. Alignment reached (T2), Dated: _____ / _____ / _____.

4. Time to reach alignment in mandible (T2-T1) : _____ days
